6.4. Methods and Timing of Assessing, Recording, and Analyzing Efficacy Data

Methods and timing of assessing efficacy data are discussed in Section 3.11. Procedures for recording efficacy data are discussed in Section 13.1, and methods of analyses are discussed in Section 9.6.2.

7. ASSESSMENT OF SAFETY

In this study, safety will be assessed by qualified study staff by evaluating the following: reported adverse events, clinical laboratory test results, vital signs measurements, ECG findings, physical examination findings (including body weight and height measurements), and suicidality (as assessed by changes from baseline in C-SSRS scores) and premature discontinuations from the study.

During the conduct of the study, an independent DSMB will review unblinded accumulating safety data on a regular basis to ensure the continuing safety of the study patients and study conduct issues.

The DSMB will meet monthly until 40 patients from each study group (i.e. a total of 160 patients) will have been exposed to their respective full dose for at least 3 months. Conditional on the absence of significant emerging safety concerns, enrolment in all the study arms will be approved to continue by the DSMB. The DSMB will then continue to meet at least bi-monthly, or as decided by the DSMB, throughout the study. The DSMB can call a meeting at any time based on safety concerns, and decisions about discontinuing patients, should that happen, will be explained in a report to all sites and patients.

The DSMB will be composed of independent physicians with expertise in the relevant therapeutic field and other relevant experts, such as a statistician. The DSMB will receive safety data periodically in an unblinded fashion. They will have the right to recommend discontinuation of the study for safety reasons.

DSMB sessions can be open or closed. During open sessions, representatives of the sponsor and the Steering Committee may be present and information is provided and discussed in a blinded fashion. During closed sessions, the only participants are members of the DSMB and the designated unblinded statistician (if approved to be present).

The DSMB chairperson will communicate with the sponsor in regard to issues resulting from the conduct and clinical aspects of the study. The sponsor will work closely with the committee to provide the necessary data for review.

7.1. Adverse Events

7.1.1. Definition of an Adverse Event

An adverse event is any untoward medical occurrence in a subject administered a pharmaceutical product, regardless of whether it has a causal relationship with this treatment.

In this study, any adverse event occurring after the clinical study patient has signed the informed consent form should be recorded and reported as an adverse event.

An adverse event can, therefore, be any unfavorable and unintended physical sign, symptom, or laboratory parameter that develops or worsens in severity during the course of the study, or significant worsening of the disease under study or of any concurrent disease, whether or not considered related to the study drug. A new condition or the worsening of a pre-existing condition will be considered an adverse event. Stable chronic conditions (such as arthritis) that

are present before study entry and do not worsen during the study will not be considered adverse events.

New symptoms of HD or deterioration of previously existing symptoms should be recorded as an adverse event only if the presentation and/or outcome is more severe than would normally be expected from the normal course of the disease in a particular subject.

Accordingly, an adverse event can include any of the following:

- intercurrent illnesses
- physical injuries
- events possibly related to concomitant medication
- significant worsening (change in nature, severity, or frequency) of the disease under study or other pre-existing conditions. (Note: A condition recorded as pre-existing that is intermittently symptomatic [e.g., headache] and which occurs during the study should be recorded as an adverse event.)
- drug interactions
- events occurring during diagnostic procedures or during any washout phase of the study
- laboratory or diagnostic test abnormalities that result in the withdrawal of the patient from the study, are associated with clinical signs and symptoms or a serious adverse event, or require medical treatment or further diagnostic work-up, or are considered by the investigator to be clinically significant. Note: Abnormal laboratory test results at the screening visit that preclude a patient from entering the study or receiving study treatment are not considered adverse events, but will be evaluated to monitor data from patients who do not meet screening criteria.
- all events of possible drug-induced liver injury with hyperbilirubinemia (defined as AST or ALT ≥ 3 times the ULN, plus either bilirubin ≥ 2 times the ULN or International Normalized Ratio [INR] > 1.5) or Hy's Law events require immediate study treatment cessation and reporting as a serious adverse event.

7.1.2. Recording and Reporting Adverse Events

For adverse event recording, the study period is defined for each patient as that time period from signature of the informed consent form through the end of the follow-up period. For this study, the follow-up period is defined as 1 month following the last dose of study medication

All adverse events that occur during the defined study period must be recorded on the source documentation and transcribed onto the CRF, regardless of the severity of the event or judged relationship to the study drug. For serious adverse events, the Serious Adverse Event Form must also be completed and the serious adverse event must be reported immediately (see Section 7.1.5.3.1).

At each contact with the patient, the investigator or designee must query the patient for adverse events by asking an open-ended question such as, "Have you had any unusual symptoms or medical problems since the last visit? If yes, please describe." All reported or observed signs and

symptoms will be recorded individually, except when considered manifestations of a medical condition or disease state. A precise diagnosis will be recorded whenever possible. When such a diagnosis is made, all related signs, symptoms, and any test findings will be recorded collectively as a single diagnosis on the CRF and, if it is a serious adverse event, on the Serious Adverse Event Form.

The clinical course of each adverse event will be monitored at suitable intervals until resolved or stabilized or returned to baseline, or until the patient is referred to the care of a health care professional, or until a determination of a cause unrelated to the study drug or study procedure is made.

The onset and end dates, duration (in case of adverse event duration of less than 24 hours), action taken regarding study drug, treatment administered, and outcome for each adverse event must be recorded on the source documentation and transcribed onto the CRF.

The relationship of each adverse event to study drug treatment and study procedures, and the severity and seriousness of each adverse event, as judged by the investigator, must be recorded as described below.

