3.6.2. Early Termination (ET)

An ET visit should be completed for all patients who prematurely terminate treatment or who become pregnant (see Section 3.11.4 for details of procedures).

Early termination refers to the study drug termination and not termination of the patient from the study. Patients will be asked to continue all scheduled visits and safety assessments after study drug discontinuation (with the exception of drug dispensing and accountability, pregnancy testing, and pharmacokinetic sampling).

Patients in the 1.5 mg/day (high dose) treatment arm, whose treatment with laquinimod was discontinued, were invited to attend an early termination visit (to return study medication and perform drug accountability). At this visit, only safety assessments were to be completed. These included vital signs, clinical laboratory tests, pregnancy test, adverse event inquiry, drug accountability, review of concomitant medication, and C-SSRS (see also Section 3.11.3.1.5). Patients were asked to continue scheduled follow up safety visits per the current schedule.

Women of child bearing potential should continue using 2 acceptable contraception methods up to 30 days after the last dose of study medication has been administered.

Moderate/strong CYP3A4 inhibitors are disallowed during the 30 days after the last laquinimod dose has been administered (see [Appendix B](#)).

Plasma levels of drugs that are CYP1A2 substrates may decrease when combined with laquinimod and within 30 days after the last laquinimod dose, rendering these drugs less effective (see [Appendix C](#)).

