Early termination refers to the study drug termination and not termination of the patient from the study. Patients in the 1.5 mg/day (high dose) treatment arm, whose treatment with laquinimod was discontinued, were invited to attend an early termination safety visit to return study medication and perform drug accountability. At this visit, only safety assessments (vital signs, clinical laboratory tests, pregnancy test, adverse event inquiry, drug accountability, review of concomitant medication, and C-SSRS) were to be conducted (see Section [3.6.2](#)), and none of the efficacy assessments. Patients were asked to continue all scheduled visits for safety assessment after study drug discontinuation.

Patients in the high dose group (1.5mg/day) who were requested to discontinue study drug before week 52, but who continue to attend scheduled study visits for safety assessment, are not considered to have completed the study.

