7.1.5.3. Reporting a Serious Adverse Event

7.1.5.3.1. Investigator Responsibility

To satisfy regulatory requirements, all serious adverse events (as described in Section 7.1.5.1) that occur during the study period (including the protocol-defined follow-up period), regardless of judged relationship to treatment with the study drug, must be reported to the sponsor by the investigator within 24 hours of becoming aware of it. Completing the serious adverse event form and reporting the event must not be delayed, even if not all the information is available. The investigator does not need to actively monitor subjects for adverse events once the study has ended. Serious adverse events occurring to a patient after the defined study period should be reported to the sponsor only if the investigator becomes aware of them.

The serious adverse event form should be sent to the Teva local safety officer (LSO) or other designated personnel (a contract research organization [CRO] in a country without a Teva LSO). Contact information is in the Clinical Study Personnel Contact Information section. The LSO will forward the report to the sponsor's Global Patient Safety & Pharmacovigilance Department.

The following information should be provided to record the event accurately and completely:

- study number TV5600-CNS-20007 (LEGATO-HD)

Clinical Study Protocol with Am 04

- investigator and investigational center identification
- patient number
- onset date and detailed description of adverse event
- investigator's assessment of the relationship of the adverse event to the study drug (no reasonable possibility, reasonable possibility)

Additional information may include the following:

- age and sex of patient
- date of first dose of study drug
- date and amount of last administered dose of study drug
- action taken
- outcome, if known
- severity
- explanation of assessment of relatedness
- concomitant therapy (including doses, routes, and regimens) and treatment of the event
- pertinent laboratory or other diagnostic test data
- medical history
- results of dechallenge/rechallenge, if known
- for an adverse event resulting in death:
 - cause of death (whether or not the death was related to study drug)
 - autopsy findings (if available)

The investigator is responsible for ensuring that the IEC/IRB is also informed of the event, in accordance with local regulations.

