 - additional investigations and follow-up per the investigator's discretion or sponsor's request

Necessary medical procedures including repeat labs will be performed based on clinical needs determined by the treating physician's judgement.

9. Guidance on monitoring subjects with CPK increase

- In case of CPK results $>ULN$, troponin and creatine kinase MB isoenzyme (CK-MB) will be tested by the central laboratory.
- In case of CPK $>10\times ULN$, an unscheduled visit to assess urine myoglobin will be required. The following blood tests will be repeated at the unscheduled visit: CPK, blood urea nitrogen, creatinine, electrolytes including potassium, calcium, phosphate.

10. Acute Coronary Syndrome, Myocardial Infarction or Any Major Cardiovascular Event

Patients who experience acute coronary syndrome, myocardial infarction or any major cardiovascular event will permanently discontinue treatment with study medication. Patients will be asked to continue all scheduled visits for safety assessment.

11. Liver Impairment

Patients who develop liver disease associated with liver functional impairment while participating in the study should stop study medication.

12. Renal Impairment

Patients who develop chronic renal disease associated with moderate-severe functional impairment, defined as estimated CrCl <60 mL/min/1.73 m², while participating in the study should stop study medication temporarily until normalization of renal function or confirmation of renal impairment diagnosis. In case moderate-severe renal impairment is diagnosed, the patient will permanently discontinue treatment with study medication.

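### The adverse-event recording period closes 1 month after the last dose, while patients who stop drug early are kept on scheduled safety visits until Week 56

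*Protocol*

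**What the plan says.** Section 7.1.2 fixes the recording window: "the study period is defined for each patient as that time period from signature of the informed consent form through the end of the follow-up". It then sets the length of that follow-up: "For this study, the follow-up period is defined as 1 month following the last dose of study medication". The duty to record is tied to the window: "All adverse events that occur during the defined study period must be recorded on the source documentation and transcribed onto the CRF". Section 7.1.5.3.1 attaches the 24-hour SAE duty to the same period, and for later events says: "Serious adverse events occurring to a patient after the defined study period should be reported to the sponsor only if the investigator becomes aware of" (such events).

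Section 3.6.2, added by Amendment 04, describes how long patients stay: "Early termination refers to the study drug termination and not termination of the patient from the study", and "Patients will be asked to continue all scheduled visits and safety assessments after study drug discontinuation". Section 3.11.3.1.5 says the same of the 1.5 mg arm: "Patients were asked to continue all scheduled visits for safety assessment after study drug discontinuation". Appendix A item 10 says it of patients who have a major cardiovascular event: "Patients will be asked to continue all scheduled visits for safety assessment".

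Other text sets no 1-month limit. Section 7.1.1 has any event after consent recorded and gives no end date. Section 7.1.2 itself requires an AE query at every contact. The synopsis and section 9.8.1 speak of adverse events throughout the study. Section 7.1.6 requires ischaemic cardiac events, cerebrovascular events and deaths to be reported within 24 hours, with no window.

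**The concern.** The 1-month rule was evidently written for a patient whose last dose and last visit are 4 weeks apart. Once stopping drug no longer means leaving the study, the two dates can be many months apart, and the protocol asks patients to attend safety visits whose findings it does not clearly require to be entered.

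Two sites can act differently and both claim compliance. One follows section 7.1.1 and records everything; the other follows the explicit end date in 7.1.2 and stops. AE counts off drug would then depend on the site and on the date of drug stop. The 1.5 mg patients matter most here. After drug stop they were followed for safety only, because of a signal in the MS trials for which section 1.4.1.2.7 reports no known mechanism and no time-to-event pattern.

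**Working it through.** **Inputs.** Treatment lasts 52 weeks and the follow-up visit is at Week 56 ± 5 days (Table 3). The recording window ends 1 month after the last dose (7.1.2). Scheduled contacts are at Weeks 4, 13, 19 (telephone), 26, 39, 52 and 56 (Table 3). The 1.5 mg arm has 30 patients (3.1). One month = 365.25 / 12 / 7 = 4.35 weeks.

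**The rule for a completer.** Week 52 + 4.35 = Week 56.35, which lies inside the Visit 9 window (Week 55.3 to Week 56.7). For completers the window and the schedule agree.

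**The rule for an early stopper.** For a drug stop at Week s and a last visit at Week E, the share of post-drug follow-up outside the window is 1 − 4.35 / (E − s).

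| Drug stop | Weeks to Week 56 | Weeks outside | Share outside (E = 56) | Share outside (E = 52) |
|---|---|---|---|---|
| Week 13 | 43 | 38.7 | 90% | 34.7 / 39 = 89% |
| Week 26 | 30 | 25.7 | 86% | 21.7 / 26 = 83% |
| Week 39 | 17 | 12.7 | 74% | 8.7 / 13 = 67% |

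For a stop at Week 13 the window closes at Week 17.35, so all five remaining contacts (Weeks 19, 26, 39, 52 and 56) fall after it. More than half of the follow-up is outside for any stop before Week 56 − 2 × 4.35 = 47.3 (Week 43.3 if E = 52).

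**An average.** The protocol gives no distribution of stop times. If they were uniform over Weeks 0–52 (an assumption), mean post-drug time to Week 56 would be 56 − 26 = 30 weeks, and the pooled share outside would be 25.65 / 30 = 86%. The mean of the per-patient shares is lower: 1 − (4.35 / 52) × ln(56 / 4) = 78%.

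**Were such visits foreseen?** Yes. Section 7.2 waives pregnancy tests for early-terminated subjects whose last dose was more than 30 days before the visit. Pregnancy testing was adjusted for these patients; the AE window was not.

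**The case against.** The best defence is that the protocol, read as a whole, keeps AE recording going. Section 7.1.1 has no end date, 7.1.2 requires a query at each contact and says reported signs and symptoms are recorded, and the synopsis and 9.8.1 say throughout the study. Section 3.6.2 lists what stops after drug discontinuation, and AE inquiry is not on the list. This shows that many sites would probably keep recording. It does not remove the conflict, because 7.1.2 is the operative section and gives an explicit end. The Table 3 wording on treatment and follow-up periods does not settle it, since 7.1.2 is where the follow-up period is defined.

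A 1-month window is also not unreasonable pharmacologically. With the half-life of about 80 h in section 1.3.2.1, one month (about 730 h) is roughly 9 half-lives. That argues for tabulating late events separately, not for leaving their recording unclear.

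Three stronger readings are tempting and are not supported:

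- **Late SAEs are lost.** Section 7.1.5.3.1 keeps them reportable once the investigator knows of them, which is likely at a safety visit. What lapses is the mandatory 24-hour duty.
- **Late cardiovascular events are missed.** Section 7.1.6 covers ischaemic cardiac events, cerebrovascular events and deaths with no time limit.
- **Every early stopper is affected.** Pregnant patients leave scheduled follow-up (Appendix A item 5), patients with a malignancy are discontinued from the study (item 6), and patients may withdraw altogether (4.3). Continued attendance is requested, not assured.

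**Conclusion.** The point holds as an internal conflict between a stated recording window and the follow-up that the design now asks for. Its reach is mainly AEs outside section 7.1.6 that arise more than 1 month off drug, together with the lapse of the mandatory 24-hour clock for SAEs in that time.

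About 90%, 86% and 74% of the time to Week 56 falls outside the window for stops at Weeks 13, 26 and 39. A reader might take these figures, or the pooled 86%, as the share of events missed. They are shares of off-drug calendar time, and the averages also rest on an assumed uniform stop time. The documents give no basis for an event count, and they do not show that the DSMB review or the safety objective would rest on truncated data. The likely harm is uneven AE capture between sites.

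Those affected are patients who stop early and stay in the study: at most 30 in the 1.5 mg arm, some of whom may already have finished treatment, and an unknown number in the other arms.

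**What to change.** In sections 7.1.2 and 7.1.5.3.1, define the AE/SAE study period as running from consent to the later of (a) 1 month after the last dose and (b) the patient's last study visit or contact. Flag events with onset more than 1 month after the last dose, so that they can be tabulated apart from on-treatment events.

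The cost is a one-sentence definition used in both sections and a flag in the AE dataset. AEs are already asked about at these visits, so no new procedure is needed. The downside is some extra AE entry for patients off drug.

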7.1.3. Severity of an Adverse Event

The severity of each adverse event must be recorded as 1 of the choices on the following scale:

- Mild:** No limitation of usual activities
- Moderate:** Some limitation of usual activities
- Severe:** Inability to carry out usual activities

7.1.4. Relationship of an Adverse Event to the Study Drug

The relationship of an adverse event to the study drug is characterized as follows:

Term	Definition	Clarification
No reasonable possibility (not related)	This category applies to adverse events which, after careful consideration, are clearly due to extraneous causes (disease, environment, etc.) or to adverse events, which, after careful medical consideration at the time they are evaluated, are judged to be unrelated to the study drug.	The relationship of an adverse event may be considered “no reasonable possibility” if it is clearly due to extraneous causes or if at least 2 of the following apply: it does not follow a reasonable temporal sequence from the administration of the test drug. it could readily have been produced by the patient’s clinical state, environmental or toxic factors, or other modes of therapy administered to the patient. it does not follow a known pattern of response to the test drug. it does not reappear or worsen when the drug is re-administered.
Reasonable possibility (related)	This category applies to adverse events for which, after careful medical consideration at the time they are evaluated, a connection with the test drug administration cannot be ruled out with certainty nor felt with a high degree of certainty to be related to the study drug.	The relationship of an adverse event may be considered “reasonable possibility” if at least 2 of the following apply: it follows a reasonable temporal sequence from administration of the drug. it cannot be reasonably explained by the known characteristics of the patient’s clinical state, environmental or toxic factors, or other modes of therapy administered to the patient. it disappears or decreases on cessation or reduction in dose. There are important exceptions when an adverse event does not disappear upon discontinuation of the drug, yet drug-relatedness clearly exists. it follows a known pattern of response to the test drug.

7.1.5. Serious Adverse Events**7.1.5.1. Definition of a Serious Adverse Event**

A serious adverse event is an adverse event occurring at any dose that results in any of the following outcomes or actions:

- death
- a life-threatening adverse event (ie, the patient was at immediate risk of death from the event as it occurred); does not include an event that, had it occurred in a more severe form, might have caused death
- inpatient hospitalization or prolongation of existing hospitalization means that hospital inpatient admission and/or prolongation of hospital stay were required for treatment of an adverse event, or that they occurred as a consequence of the event.

Hospitalizations scheduled for an elective procedure or for treatment of a pre-existing condition that has not worsened during participation in the study will not be considered serious adverse events.

- persistent or significant disability or incapacity (refers to a substantial disruption of one's ability to conduct normal life functions)
- a congenital anomaly/birth defect
- an important medical event that may not result in death, be life-threatening, or require hospitalization, but may jeopardize the patient and may require medical intervention to prevent one of the outcomes listed in this definition. Examples of such events are intensive treatment in an emergency room or at home for allergic bronchospasm; blood dyscrasias or convulsions that do not result in hospitalization; or the development of drug dependency or drug abuse. Note: Any suspected transmission of an infectious agent via a medicinal product is considered an important medical event.

An adverse event that does not meet any of the criteria for seriousness listed above will be regarded as a nonserious adverse event.

